Past and current medical conditions, medications	×											-	Within 12 months prior to the Screening visit, history, or current alcohol, substance, or drug abuse, relevant medication including medication history for the treatment of SLE and CLE and flare history.

				DE	DBPC Treatment Period	atmeni	t Perio	 			Safety Follow- up ^c	ety c	Notes
Assessments and Procedures (Weeks)	Screening -7 to -5	0	2	4	80	12	16	20	24/ EOTª	ЕТЬ	25	26	5-Week Screening Period with the possibility to expand by an additional 2 weeks if needed to repeat a laboratory test or due to an unanticipated event, upon Medical Monitor approval. Minimum Screening period is 2 weeks.
Study Day	-49 to -1	1	15	53	22	85	113	141	169		176	183	
Visit Window (Days)			+ 3	€∓	+3	+3	± 3	+ 3	± 3	£ +	+ 3	+ 3	
SCLE or DLE diagnosis: Historical pathology report for skin biopsy OR Fresh skin biopsy	×												Participants with cutaneous lupus lesions unsuitable for biopsy (e.g., malar rash, bridge of the nose) will be evaluated by skin photography instead. See Inclusion criterion 3, Section 5.1.
Documentation of SLE, SCLE, and/or DLE classification criteria	×												See Section 5.1.
Chest imaging	×												See Exclusion criterion 32, Section 5.2.
SARS-CoV-2 test	×												Only if required. See Section 5.2.
Serum pregnancy test	×												WOCBP only (see Section 5.1).
Serum virology (Hepatitis B and C screening, HIV)	×	×	×	×	×	×	×	×	×	×		×	See Section 5.2. Screening: all participants Other visits: only for participants positive for anti HBc antibody and/or anti-HBs antibody with non-detectable HBV DNA at Screening (see Section 8.2.4. and Appendix 5).
TB assessment	×												See Section 5.2.
TSH	×												See Section 5.2.
FSH and estradiol	×												Women of nonchildbearing potential only to determine postmenopausal status. See Section 8.2.4.
ANA	×												See Inclusion criterion 8, Section 5.1.
CCI													

				DBI	DBPC Treatment Period	tment	Perioc				Safety Follow- up ^c	≥ \$	Notes
Assessments and Procedures (Weeks)	Screening -7 to -5	0	7	4	ω	2	9		24/ EOTª	ΕT _β	10 25	56	5-Week Screening Period with the possibility to expand by an additional 2 weeks if needed to repeat a laboratory test or due to an unanticipated event, upon Medical Monitor approval. Minimum Screening period is 2 weeks.
Study Day	-49 to -1	1	15	59	22	85	113 1	141	169	•	176	183	
Visit Window (Days)			± 3	± 3	± 3	± 3	±3	±3	± 3	+ 3	+ 3	+ 3	

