 - Positive HBV surface antigen, or positive HBV core Ab with negative HBV surface Ab and reflexive detectable HBV DNA NAAT at Screening, or no history of HBV vaccination with positive HBV surface and/or core Abs and reflexive detectable HBV DNA NAAT at Screening.
- 14. Any of the following:

a. History of active TB.

Note: patients with a history of active or latent TB who have documented evidence of appropriate treatment and with no history of re-exposure since their treatment was completed would not be required to undergo the protocol-specific TB testing for PPD, QuantiFERON test, or T-SPOT test, but would still require a Baseline chest x-ray to rule out active TB and documentation of completed treatment.

- b. Current diagnosis of active TB.
- c. Untreated LTBI.
- d. Undergoing current treatment for LTBI.
- e. Participants with current household contacts with active TB.

In the absence of an active TB diagnosis, or clinical features consistent with an active TB diagnosis, LTBI is determined by any of the following:

- Prior TB skin test with purified protein derivative with induration ≥ 5 mm (unless vaccinated with Bacille Calmette-Guérin).
- Prior positive T-SPOT.TB (Elispot) result.
- Positive QuantiFERON test, either at Screening, or with documented past results.

Note: All participants, except those who have previously completed appropriate and documented LTBI treatment, must undergo QuantiFERON testing during Screening. Participants with indeterminate or positive QuantiFERON results that may represent a false positive result by the Investigator with no clinical features consistent with active TB, will be evaluated with either a repeat QuantiFERON test (local or central laboratory test) or a T-SPOT (local laboratory test) TB at the request of the Investigator. In the case of a negative QuantiFERON or T-SPOT.TB result, the participant may be enrolled after approval by the study eligibility team. If the repeat QuantiFERON result is indeterminate, the participant will be excluded.

- 15. History of malignancy (e.g., hematologic, skin, solid tumor) ≤ 10 years prior to Screening Visit, except adequately treated basal cell or squamous cell carcinomas of the skin (≤ 3 lesions requiring treatment in lifetime) or adequately treated carcinoma in situ/cervical intraepithelial neoplasia of the uterine cervix.

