- 16. Any major surgery such as abdominal, thoracic, or joint replacement surgeries \leq 6 weeks prior to Screening Visit or planned major surgery during the study (including Follow-up).
- 17. History of alcohol or drug abuse ≤ 1 year prior to Screening Visit as per Investigator opinion.
- 18. History of splenectomy or functional asplenia.

CC

20. Any condition that could interfere with study objectives, conduct, or evaluation in the opinion of the Investigator or Sponsor/designee.

Prior/Concomitant Therapy (See Appendix 6 for further details)

- 21. Known hypersensitivity to any study intervention, component, or placebo.
- 22. Initiation or dose change of anticoagulation or antiplatelet therapy ≤ 4 weeks prior to Screening Period.

$\overline{\mathsf{CC}}$

- An unstable dose ≤ 3 months prior to Day 1, except for medications administered short term to treat acute symptoms (e.g., emesis), which is allowed.
- 24. The use, initiation, or dose change in the following therapies ≤ 2 weeks prior to Screening:
 - a. Use of CS exceeding 30 mg daily prednisone-equivalent for SLE and CLE (SCLE and/or DLE), including but not limited to oral, topical CSs Class I, and augmented betamethasone dipropionate 0.05% gel or ointment, intramuscular, or injectable CS (Table 11).
 - b. Use of topical calcineurin inhibitors more than 1 time per day.
 - c. Initiation or dose change of angiotensin-converting enzyme inhibitors or angiotensin receptor blocker, or NSAIDs, or use of NSAIDs above maximum prescribed dose per local label.
- 25. The initiation, use, or change in the following therapies \leq 4 weeks prior to Screening:
 - a. Vaccination with live or live attenuated virus vaccine.
 - b. Use of thalidomide or lenalidomide.
 - c. Use of intralesional therapies.
 - d. Use of tripterygium and total glucosides of paeony.
- 26. The initiation, use of a dose exceeding the maximum specified dose (see Appendix 6) or change in therapies < 8 weeks prior to Screening for any medication considered to have immunomodulating and/or immunosuppressant properties (e.g., antimalarials, MTX, 6-mercaptopurine, sulfasalazine, MMF, or sodium, AZA, dapsone, or retinoids). A stable dose of leflunomide is not exclusionary; however, participants having changed their dose or discontinued leflunomide must have done so at least 8 weeks prior to Screening.
- 27. The initiation, use or change in the following therapies \leq 12 weeks prior to Screening:

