8.2.4 Clinical Safety Laboratory Assessments

- Blood and urine samples will be collected for the clinical laboratory tests listed in Appendix 5 at the time points listed in the SoA. All samples will be clearly identified and detailed in the Laboratory Manual. No fasting is required for laboratory tests.
- Repeat tests may be performed at any time during the study, as determined necessary by the Investigator or required by local regulations.
- The tests will be performed by a central laboratory with the exception of urinalysis and microscopy, urine pregnancy tests, ESR, reflexive HBV DNA NAAT test after Screening, T-SPOT TB test (if required, see Section 5.2), QuantiFERON (only if repeated and preferred over central laboratory, see Section 5.2), SARS-CoV-2 test if required, and any applicable vaccines which will be performed by a local laboratory or locally.
- Local laboratory results are only required when central laboratory results are not available in time for study intervention administration and/or response evaluation. If a local sample is required, it is important that the sample for central analysis is obtained at the same time. Additionally, if the local laboratory results are used to make a study intervention decision or response evaluation, the results will be recorded.
- The Sponsor will receive a list of the local laboratory normal ranges before shipment of study intervention(s). Any changes to the ranges during the study will be forwarded to the Sponsor or designated organization.
- The following safety laboratory assessments will be performed at Screening only:
 - FSH and estradiol (for women of nonchildbearing potential only to determine postmenopausal status).
 - Serum pregnancy test (for women of childbearing potential only).
 - Serum virology (Exclusion Criterion 12, Section 5.2), except for reflex testing.
 - Thyroid stimulating hormone
- HBV DNA will be conducted every 4 weeks up to Week 24/ End of Treatment and at end of Safety follow-up (Week 26) for participants with positive anti-HBc antibody and/or anti-HBs antibody with non-detectable HBV DNA at Screening.
- Pregnancy testing (serum or highly sensitive urine, as required by local regulations) will be conducted at monthly intervals during study intervention administration.

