Appendix 5 Clinical Laboratory Tests

The protocol-required clinical laboratory assessments are in the following table:

Table 5 Clinical Laboratory Assessments

Laboratory Assessments	Parameters			
Hematology	Platelet count		MCV	White Blood Cell Count with Differential:
	Hemoglobin		MCH	Neutrophils
	Hematocrit		ESR, CRP	Lymphocytes
	RBC count		Coagulation profile (INR, PT, aPTT, etc.)	 Monocytes Eosinophils Basophils
Biochemistry	Blood Urea Nitrogen	Potassium	Aspartate aminotransferase Alanine aminotransferase	Bilirubin
	Creatinine	Sodium	Gamma-glutamyl- transferase	Total Protein
	Glucose	Calcium	Alkaline phosphatase	eGFR
	Chloride	CO ₂	Albumin	
CCI				
First morning Clean-Catch Urinalysis	 Frequent reminders/instructions must be provided to ensure the urine specimen is a clean-catch from the first morning void. Urinalysis will be performed by the local laboratory. The test may be repeated in clinic if sample determined to be a "dirty urine." UPCR–Before morning of collection, provide participant with specimen cup. The participant will collect first morning void, clean-catch midstream sample at home in the morning of clinic visit and bring to the site. The sample will be sent to the central laboratory. The same sample taken for UPCR may be used to perform the urinalysis. Specific gravity. pH, glucose, protein, blood, ketones, bilirubin, urobilinogen, nitrite, leukocyte esterase by dipstick. Microscopic examination (if blood, leukocyte esterase, or protein is abnormal). 			
Other Screening Tests	 FSH and estradiol (for non-WOCBP only). Serum hCG pregnancy test (as needed for a WOCBP). Serology: hepatitis B (HBs antigen, HBsAb, HBcAb with reflexive HBV DNA NAAT) and hepatitis C (HCVAb and reflexive HCV RNA NAAT), per exclusion criteria. HIV laboratory test (either antibody or nucleic acid amplification test) Tuberculosis assessment (QuantiFERON, T-SPOT). Antinuclear antibodies. Thyroid stimulating hormone. 			
microscopy, ESR, T-S	pratory assessments will	be performed by if repeated a	oy a central laboratory, excep nd preferred over central lab urine pregnancy tests.	
PK	See Section 8.4			

Laboratory Assessments	Parameters
Pregnancy test after Screening	Urine pregnancy test: Highly sensitive urine pregnancy test. If required by local regulations, a serum testing will be done instead
Other tests	

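### The hepatitis B exclusion and the scheduled HBV DNA follow-up both miss vaccinated, anti-HBs-positive participants with detectable HBV DNA at Screening

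*Protocol*

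**What the plan says.** The hepatitis B item of criterion 13 (Protocol 5.2) has three limbs joined by 'or':

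1. "Positive HBV surface antigen", with no further condition.
2. "positive HBV core Ab with negative HBV surface Ab and reflexive detectable HBV DNA NAAT at Screening".
3. "no history of HBV vaccination with positive HBV surface" and/or core antibodies, again with detectable HBV DNA on the reflex test.

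For visits after Screening, the serum virology row of Table 1 restricts testing as follows: "Other visits: only for participants positive for anti HBc antibody and/or anti-HBs antibody with non-detectable HBV DNA at Screening". Section 8.2.4 sets the same condition for its HBV DNA schedule, which is "for participants with positive anti-HBc antibody and/or anti-HBs antibody with non-detectable HBV DNA at Screening".

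Appendix 5 lists the Screening panel as "hepatitis B (HBs antigen, HBsAb, HBcAb with reflexive HBV DNA NAAT". It does not say which antibody result triggers the reflex DNA test.

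**The concern.** The follow-up rule reads as if nobody with detectable HBV DNA at Screening can be enrolled: it names only the antibody-positive, DNA-negative group. The exclusion rule does not guarantee that, because limb 2 needs a negative anti-HBs and limb 3 needs an absence of vaccination. A vaccinated, anti-HBs-positive participant escapes both limbs even with detectable DNA.

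The result is out of order. An antibody-positive participant with no detectable virus has scheduled HBV DNA tests, while one with detectable virus, if enrolled, has none. That participant could take blinded study intervention for 24 weeks on top of background therapy, which under Section 6.8.3 may include corticosteroids up to 30 mg prednisone-equivalent daily and an immunosuppressant. A later rise in ALT would enter the liver outputs of SAP 15.3 (liver function categories, possible Hy's law cases, eDISH plots) without scheduled HBV DNA values to help interpret it.

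**Working it through.** The plan states no figure to reproduce. The check applies the written rules to every combination of five yes/no inputs: HBsAg, anti-HBs, anti-HBc, HBV DNA detectable, and history of HBV vaccination (2^5 = 32 combinations).

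- Excluded = HBsAg+ OR (anti-HBc+ AND anti-HBs− AND DNA+) OR (not vaccinated AND (anti-HBs+ OR anti-HBc+) AND DNA+).
- Scheduled for on-study HBV DNA = (anti-HBc+ OR anti-HBs+) AND DNA not detectable at Screening.

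The 16 HBsAg-positive combinations are all excluded by limb 1. The 16 HBsAg-negative ones divide into 8 with and 8 without detectable DNA. Six of the 8 DNA-detectable combinations have at least one positive antibody:

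| Anti-HBc | Anti-HBs | Vaccinated | Limb 2 | Limb 3 | Excluded | HBV DNA scheduled |
|---|---|---|---|---|---|---|
| + | − | no | met | met | yes | n/a |
| + | − | yes | met | not met | yes | n/a |
| − | + | no | not met | met | yes | n/a |
| + | + | no | not met | met | yes | n/a |
| − | + | yes | not met | not met | **no** | **no** |
| + | + | yes | not met | not met | **no** | **no** |

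So 4 of the 6 are excluded and 2 are admitted.

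Of the 8 HBsAg-negative combinations without detectable DNA, none is excluded. Six are antibody-positive, and all six are scheduled for HBV DNA. Admitted antibody-positive combinations therefore number 6 + 2 = 8. Six have scheduled HBV DNA; the two without it are the same two that pass the exclusion with detectable DNA.

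Two further checks:

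- **What the vaccination condition does.** Limb 3 already requires detectable DNA, so DNA-negative vaccinees would not be excluded with or without the condition. Evaluating limb 3 without it changes the outcome of only the last two rows above. Its sole effect is on DNA-detectable vaccinees.
- **Antibody-negative, DNA-detectable participants** (the remaining 2 of the 8) are also neither excluded nor scheduled. Because the DNA test is reflexive, they would not normally be found, so the statement is confined to antibody-positive entrants.

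**The case against.** The strongest reply is that criterion 13 is not the whole eligibility process. Criterion 20 allows exclusion for "Any condition that could interfere with study objectives, conduct, or evaluation in the opinion of the Investigator or Sponsor/designee", and criterion 3 does so for conditions judged an inappropriate risk. Section 5 has the Medical Monitors re-evaluate and confirm eligibility from a submitted packet, and criterion 30 excludes AST or ALT above 2.5 × ULN. After entry, Table 1 schedules chemistry at every clinic visit from Day 1 to Week 24, at early termination and at Week 26. Section 8.3.8 gives actions for raised transaminases, including a search for other causes, and Section 8.2.4 permits repeat tests at any time.

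This stands in part. A reader might infer that the trial will knowingly enrol such participants, that they can have no HBV DNA test on study, or that a later ALT rise would be taken for drug injury. The documents do not support any of these. The discretionary criteria may stop entry, an unscheduled test is allowed, and a positive Screening DNA result would already be on file. But criteria 3 and 20 depend on opinion, and Medical Monitor review applies the criteria as written. Chemistry detects liver injury rather than viral replication. None is an HBV DNA rule, and none changes the condition in Table 1 and Section 8.2.4.

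A second reply is that the wording may be deliberate. Appendix 10 records that limb 3 was edited after a regulator's inquiries and that the DNA monitoring was aligned with a national guideline. Neither source is available here. The documents give no reason for treating vaccinees with detectable DNA differently, and an intention to admit them would still leave them outside the follow-up rule.

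Third, Appendix 5 could be read as running the reflex DNA test only on a positive anti-HBc. The anti-HBc-negative combination would then have no Screening DNA result and would not be seen. Limb 3 and the follow-up rule, however, both presuppose a DNA result in participants positive for anti-HBs. On either reading the vaccinated participant positive for both antibodies remains in the gap.

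**Conclusion.** The concern holds as a mismatch between two stated rules. By its wording, criterion 13 does not exclude HBsAg-negative, anti-HBs-positive, vaccinated participants with detectable HBV DNA, whether anti-HBc is positive or negative. Table 1 and Section 8.2.4 schedule no HBV DNA follow-up for them. The size in logical terms is 2 of 6 combinations (1 observable combination if the reflex test is triggered by anti-HBc alone).

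The size in people cannot be derived. The documents give no prevalence of anti-HBc, of detectable DNA in HBsAg-negative participants, or of vaccination. The number is probably small, because several uncommon features must coincide, but that is a judgement and no head count is offered. The point rests on a literal reading of the three limbs and on a Screening DNA result being available for antibody-positive participants. It matters for participant safety and for interpreting individual liver signals; it has no bearing on the power or type I error of the primary analyses.

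A reader might also infer that the vaccination condition is simply wrong and must go. The documents show that it creates the gap; they do not settle which clinical rule should apply.

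**What to change.** Reconcile criterion 13 in Section 5.2, the serum virology row of Table 1, and the HBV DNA item in Section 8.2.4, so that exclusion and scheduled follow-up together account for every antibody-positive participant with a Screening HBV DNA result. Whether that is done through the exclusion rule, the follow-up rule or both is a clinical decision for the sponsor. The same amendment should state in Appendix 5 which antibody results trigger the reflex DNA test, so that it is clear who has a Screening result.

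The cost is a short wording amendment. The reflex test is already part of Screening, so the only operational consequence is possibly a very small number of additional screen failures or HBV DNA tests. No statistical analysis needs to change.

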Appendix 2 provides details related to study closure and site termination.

5 Study Population

The criteria in Sections 5.1 and 5.2 are designed to enroll only participants, who are appropriate for the study; thereby, ensuring the study fulfills its objectives. All relevant medical and nonmedical conditions are considered when deciding whether a participant is suitable for this study.

Prospective approval of protocol deviations to inclusion and exclusion criteria, also known as protocol waivers or exemptions, is not permitted.

Before performing any study assessments that are not part of the participant's routine medical care, the Investigator will confirm that the participant or the participant's legal representative has provided written informed consent, as indicated in Appendix 2.

Eligibility will be evaluated by the study Investigator, and re-evaluated, and confirmed by the Sponsor or designee Medical Monitors comprising the study eligibility team. Additional lupus experts may be consulted during the eligibility process (e.g., to confirm CLE subtypes

diagnosis). Sites will be required to submit an eligibility packet (consisting of an eligibility checklist and appropriate documentation) for consented and potential eligible participants. The participant's eligibility will be assessed at a Screening Visit, which will occur up to 5 weeks prior to the Randomization Visit (Day 1). When a laboratory test must be repeated during the Screening Period or an unanticipated event occurs, the Screening Period can be extended to 7 weeks after discussion with the Medical Monitor. See Table 1 for a list of assessments performed at Screening to determine the eligibility of the participant to take part in the study. Participants will be randomized into the study when eligibility is confirmed.

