 - a. Use of abatacept, antitumor necrosis factor alpha agents, intravenous Ig, plasmapheresis, CYC, or other disease modifying, immunosuppressive, or immunomodulatory therapies not otherwise specified in protocol.
- 28. The initiation, use or change in the following therapies \leq 24 weeks prior to Screening, unless a different time frame is indicated:
 - a. Use of alkylating agents other than CYC (e.g., chlorambucil).

- b. B cell depleting/modulating therapy such as anti-CD20 agents (e.g., belimumab [≤ 16 weeks prior to Screening], atacicept, telitacicept), dual or other anti-B Lymphocyte Stimulator /proliferation inducing ligand neutralizing therapies (see Appendix 6).
- c. IL-12/IL-23 pathway inhibitors (e.g., ustekinumab).
- d. Anti-IL-6 receptor (tocilizumab, sarilumab) or anti-IL-6 (siltuximab).
- e. Anti-IL-1 agents.
- f. Type 1 IFN pathways inhibitors (e.g., anifrolumab).
- g. JAK-STAT pathway inhibitors (e.g., tofacitinib): ≤ 4 weeks prior to Screening.
- h. Vaccination with a subunit or inactivated vaccine (e.g., influenza virus, S. pneumoniae): < 2 weeks prior to Day 1. Vaccination during the study is allowed providing that vaccination completes at least 2 weeks before any study visit. For SARS CoV-2 vaccine or vaccine series see Section 2.3.2.

Prior/concurrent Clinical Study Experience

29. Treatment with other investigational agents within the last 12 weeks or 5 half-lives or as per washout requirement from the previous protocol, whichever is longest, prior to Screening Visit (e.g., small molecules such as Bruton's tyrosine kinase inhibitors).

Diagnostic Assessments

- 30. Clinically significant or predefined abnormalities in laboratory tests at Screening Visit:
 - AST, ALT, or alkaline phosphatase $> 2.5 \times ULN$;
 - Total bilirubin $> 1.5 \times ULN$;
 - Hemoglobin < 5.0 mmol/L (9 g/dL), white blood cells < 2.5×10^9 /L, absolute neutrophil count < 1,500/mm³, or platelets < 75×10^9 /L, unless any of these are attributable to active SLE;
 - Or thyroid stimulating hormone $< 0.01 \text{ mIU/L or} \ge 7.1 \text{ mIU/L}$ per central laboratory results.
- 31. Signs of significant chest imaging (chest X-ray, CT, MRI) abnormality (e.g., interstitial lung disease, active TB). Results from a chest imaging study ≤ 3 months of Screening are acceptable if no reason to suspect clinical changes.

Other Exclusions

32. Legal incapacity or limited legal capacity.

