15.3 Clinical Laboratory Evaluation

All laboratory values will be reported in SI units. Time window will be applied to laboratory assessments (see section 9.7).

Laboratory values (including corresponding normal ranges) from the central laboratory will be used for summary statistics and shift tables.

In case both central and local labs are collected, summary statistics will be based on central lab collected data, while summaries of worst on-treatment abnormalities will be based on both local and central lab data.

Laboratory results will be graded according to NCI-CTCAE version 5.0. Laboratory parameters which cannot be graded per NCI-CTCAE will be presented according to the categories: below normal limit, within normal limits and above normal limit (according to the laboratory normal ranges).

The definition of baseline measurement is provided in section 9.2.

Values below the detection limit will be imputed by half of the detection limit. If a text value with an "> x" is reported it will be analyzed as +1 significant digit, e.g., "> 7.2 mmol" will be analyzed as 7.3.

Quantitative data (hematology, biochemistry, coagulation and urinalysis) will be summarized using descriptive statistics (n, mean, SD, median, Q1, Q3, minimum, and maximum) of raw values and absolute changes from baseline at each on-treatment scheduled visit.

Qualitative data (hematology, biochemistry and coagulation) based on reference ranges will be described according to the categories (i.e., low, normal, high). For urinallysis parameters, the classification Normal, Trace/+, ++, ++++ will be used instead.

Abnormalities classified according to NCI-CTCAE toxicity grading version 5.0 will be described using the worst on-treatment grade. Unless otherwise specified, number of participants with missing measurements will be presented as separate category. For those parameters which are graded with two directions of toxicities such as potassium (hypokalemia/hyperkalemia), the toxicities will be summarized

CONFIDENTIAL

INFORMATION

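### Exclusion criterion 30 prints one haemoglobin limit as 5.0 mmol/L and 9 g/dL, which are different values, and nothing in the protocol or SAP says which one governs

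*Protocol*

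**What the plan says.** Criterion 30 in Protocol Section 5.2 opens with "Clinically significant or predefined abnormalities in laboratory tests at Screening Visit" and then lists limits. The haemoglobin entry is "Hemoglobin < 5.0 mmol/L (9 g/dL", with the second figure in brackets as the equivalent of the first. The haemoglobin, white-cell, neutrophil and platelet limits share one exception: "unless any of these are attributable to active SLE".

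Four other places bear on how the limit is applied.

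- Protocol Section 8.2.4 assigns laboratory work centrally: "The tests will be performed by a central laboratory with the exception of urinalysis and microscopy", followed by further exceptions. Haemoglobin is not among them. The section also says "Local laboratory results are only required when central laboratory results are not available in time".
- Protocol Section 5 has the investigator evaluate eligibility and the sponsor's or designee's Medical Monitors confirm it from a submitted packet with a checklist. On prospective approval of deviations from the criteria, it says that this, "also known as protocol waivers or exemptions, is not permitted".
- SAP Section 15.3 states "All laboratory values will be reported in SI units". It gives no haemoglobin conversion.
- SAP Section 8.2 defines a CLE-only subgroup of Cohort A with no SLE diagnosis.

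No other section gives a haemoglobin eligibility limit, a conversion factor, or a rule on which unit takes precedence.

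**The concern.** A threshold written in two units works only if the two figures are the same value. If they differ, there is a band of results on which the criterion contradicts itself, and anyone applying it must choose a figure without guidance.

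What is at stake is consistent safety screening and a clean deviation record. Protocol Section 7.1.2 makes enrolment despite an exclusion criterion a possible reason for withdrawal from study intervention. SAP Section 10.2.1 requires deviations to be documented and important ones to be tabulated. For a participant inside the band, the protocol cannot say whether a violation occurred.

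**Working it through.** **Inputs**

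- Printed limit: 5.0 mmol/L and 9 g/dL (Protocol Section 5.2, criterion 30).
- Molar mass M: not in the documents. Assumed to be the haemoglobin monomer at 16,000 to 16,200 g/mol, with 16,114 as the central value. A high value of 17,000 and the tetramer at 64,458 are included as checks.

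**Formula**

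g/dL = mmol/L × M / 10,000, with M in g/mol.

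**Step 1: try to reproduce the printed equivalence.** Setting 5.0 × M / 10,000 = 9 gives M = 9 / 5.0 × 10,000 = 18,000 g/mol. That is about 12% above the monomer (18,000 / 16,114 = 1.117) and nowhere near the tetramer. The equivalence is not reproduced.

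**Step 2: convert each figure.**

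| M (g/mol) | 5.0 mmol/L in g/dL | 9 g/dL in mmol/L | Gap in g/dL |
|---|---|---|---|
| 16,000 | 8.00 | 5.63 | 1.00 |
| 16,114 | 8.06 | 5.59 | 0.94 |
| 16,200 | 8.10 | 5.56 | 0.90 |
| 17,000 (check) | 8.50 | 5.29 | 0.50 |
| 64,458 (tetramer) | 32.2 | 1.40 | no match |

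**Step 3: test whether rounding explains it.** Read 5.0 as anything from 4.95 to 5.05 mmol/L, and 9 as anything from 8.5 to 9.5 g/dL. At M = 16,114 the first interval is 7.98 to 8.14 g/dL, which does not reach 8.5. At the top of the assumed range its upper end is 5.05 × 1.62 = 8.18 g/dL, still short. The intervals meet only when M is at least 8.5 / 5.05 × 10,000 = 16,832 g/mol, which is outside the assumed range.

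**Step 4: find the contradictory band.** Take a Screening result of 8.5 g/dL. At M = 16,114 it is 8.5 / 1.6114 = 5.27 mmol/L. It is below 9 g/dL, so it is excluded on that figure. It is above 5.0 mmol/L, so it is not excluded on the other. The same holds from about 8.1 to just under 9.0 g/dL (5.0 to just under 5.6 mmol/L).

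**Step 5: apply the exception.** Values attributed to active SLE drop out of the criterion on either figure. The conflict therefore decides eligibility only for low haemoglobin with another cause. Participants with CLE only have no SLE to which a low value could be attributed, so every such participant in the band is affected.

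**The case against.** The strongest case on the other side accepts the arithmetic and disputes the consequence.

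- **The processes are central.** Haemoglobin is a central-laboratory test, and Medical Monitors confirm eligibility from a common packet. A reader might infer from the roughly 170 sites in about 20 countries (Protocol Appendix 2) that site laboratories report in different units, so that eligibility turns on the unit a site reads or that safety screening differs by region. The documents do not support this. They do not say what units sites receive, and they describe no regional difference in screening. Region is also a stratification factor, so a regional difference in case mix would be addressed across arms by design. This part of the objection stands. It moves the problem from site practice to the text: whoever builds the checklist or the central flag must still choose between two numbers. One narrow route for local values exists, because Protocol Section 8 lets a qualifying routine-care blood count taken before consent serve for screening.
- **Few participants are likely to be affected.** The active-SLE exception removes part of the band, and criterion 20 allows discretionary exclusion. This is fair. The documents give no basis for a count. Criterion 20 does not define the limit, and the exception does not reach CLE-only participants.
- **The SAP's SI rule settles the unit.** It does not. The rule concerns reporting of results, not eligibility. The SAP itself uses g/L for haemoglobin in the severe-flare definition in Section 14.3.12, so the rule does not select mmol/L.
- **Nothing inferential depends on it.** This is correct. The exclusions from the Full Analysis Set in SAP Section 8.1 turn on cohort eligibility and BILAG scores, not on haemoglobin.

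**Conclusion.** The two printed limits conflict. With a monomer mass of 16.0 to 16.2 g/mmol they differ by 0.9 to 1.0 g/dL, or 0.56 to 0.63 mmol/L. Rounding does not close the gap and the tetramer basis does not fit. The molar mass is an assumption from outside the documents, but agreement would need 18,000 g/mol.

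The consequence is limited. For a Screening value from about 8.1 to just under 9.0 g/dL that is not attributed to active SLE, the protocol does not determine eligibility, and no waiver route exists. It has not been shown that any participant was handled inconsistently, because the checklist and the central flag are not in the documents. Sample size, power, alpha, estimands and analysis sets are unaffected. This is a minor correction. Which limit was intended cannot be settled from the text, and that decision belongs to the sponsor.

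**What to change.** The sponsor should reconcile the two figures in criterion 30 and state one limit in one unit, with its exact conversion if a second unit is kept. The same figure should go into the eligibility checklist and the central-laboratory flag. If enrolment has begun, the sponsor should record which figure has been applied so far and list any randomised participants whose Screening haemoglobin lies between the two limits without attribution to active SLE, so that deviations are classified on one rule.

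There is a precedent: the amendment history for Protocol Version 2.0 records that one of two non-equivalent unit forms of the UPCR limit was removed from the same section.

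The text change is one line plus the checklist and flag. Under Protocol Appendix 2 an amendment needs IRB/IEC approval and, where applicable, Health Authority submission, so it is sensible to bundle the correction into the next amendment.
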